8.4.1 Demographics

Age at consent, height, weight, BMI and other continuous demographic variables at baseline will be summarized descriptively. Sex, race, ethnicity and other categorical variables will be summarized using the ITT/FAS population.

BST1302-SOP-T01/v1.0/2020

8.4.2 Baseline and disease characteristics

The baseline continuous characteristics (vital signs) will be summarized descriptively for the ITT population. The baseline categorical characteristics (results of physical exams, ECG, serum chemistry, hematology and urinalysis, serology) will be summarized using frequency counts and percentages for the safety population.

8.4.3 Medical history

A summary of medical history and defined high-risk comorbidities will be presented by system organ class (SOC) and Preferred Term using the Medical Dictionary for Regulatory Activities (MedDRA) version 23.0. Medical history will be graded for severity.

8.4.4 Prior and concomitant medications

Medications used in this study will be coded by using MedDRA version 23.0.

Prior medications are defined as those medications with a start date 28 days prior to the initial screening.

Concomitant medications are defined as those medications with a start state later than 28 days prior to the initial screening and will be recorded at screening visit. At each subsequent study visit each new concomitant medication and changes to existing medications will be recorded. Subjects will be required not to utilize non-study medication or herbal supplements during the study except those deemed necessary by the site Principal Investigator (PI) or sub investigator. Any drug (e.g., over-the-counter herbal supplement, vitamins or prescription) used by the subject during the course of the trial will be recorded in the subject's source documents and on the appropriate eCRF. Per protocol section 5.2 exclusion criteria #20, subjects using any of the prohibited medications within 28 days prior to screening or planned use during the study period will be excluded from the study. However, if any prohibited medication is used during study period by any enrolled subject, it would be captured as a protocol deviation at local sites.

Prior and concomitant medications will be summarized descriptively using frequency tables by Anatomical Therapeutic Chemical (ATC) class and preferred name by treatment group on the ITT population and presented separately for the following groups:

- · Medications prior to 28 days before the initial screening.
- Concomitant medications continued after initial screening.
- Concomitant medications started at or after the initial screening.
- Prior and concomitant use of any restricted medications as described in protocol exclusion criteria.

Details for imputing missing or partial start and/or stop dates of medication are described in section 7.3.

Extent of exposure

A single dose of study product will be administered on-site by research personnel at Day 1 (Visit 2 per protocol v7.0) for all subjects. All study products will be administered via IM injection. Thus, treatment compliance will not be applicable.

Efficacy analysis

Efficacy analysis is only applicable to the secondary endpoints regarding immunogenicity described in section 4.2 and analysis methods are described in section 8.6.5 below.

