8.1. Visit 1: Screening (Day -14 to Day -2)

After providing written informed consent, each subject will be assigned a Subject ID number (840-XXX-XXX) and undergo an eligibility assessment. The following will be done during the screening period (within 14 days prior to administration of study product). Results of screening tests and procedures will be evaluated by the investigator to determine eligibility prior to enrollment and randomization. The following procedures will be performed.

- Record demographics including age, gender, race and ethnicity. Obtain contact information.
- Obtain medical history. The medical history will include the following:
 - current medical diagnoses
 - past medical diagnoses
 - hospitalizations
 - major surgical procedures
 - blood transfusions or immunoglobulin within the last 6 months
 - live vaccines within the last 28 days
 - killed vaccines within the last 28 days
 - blood or plasma donation within the last 56 days
 - allergic reactions
 - drug and/or alcohol use disorder or dependence
 - receipt of investigational drug within the last 28 days
 - Receipt of monoclonal antibody in the past
- Documentation that the subject has not received an FDA approved vaccine for COVID-19 (Subjects may receive an approved COVID-19 vaccine after completing their Day 90 visit). For Cohort 5, subjects who received a COVID-19 vaccine within 14 days prior to enrollment are excluded.
- Review concomitant medication history, including all medications taken within the last 28 days
- Review current use of contraceptive methods and recent menstrual history (female subjects only)

- Perform abbreviated PE by licensed clinician listed on the Form FDA 1572 [examples include Medical Doctor, Nurse Practitioner and Physician's Assistant]
- Obtain height and weight and calculate BMI
- Take vital signs (systolic and diastolic blood pressure, pulse rate, respiratory rate, and oral temperature)
- Obtain fasting blood samples for viral serology, clinical laboratory screening tests including SARS-CoV-2 antibodies and RT-PCR for SARS-Co-V-2
- Obtain blood sample for serum pregnancy test for women of childbearing potential
- Obtain urine sample for dipstick urinalysis and urine toxicology
- Obtain 12-lead ECG
- Perform Breathalyzer test or blood/saliva alcohol test for recent alcohol use
- Counsel both men and women of childbearing potential on the avoidance of pregnancy

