All attempts will be made to collect all data per protocol. No imputations will be conducted for missing values. Outliers identified during the PK analysis will be discussed in the analysis report.

Missing data analysis methods

Imputation rules for missing or partial adverse event start/stop dates

- If the AE start date day is missing (month and year provided) then set the date to the first of the
 month unless the month and year are the same as the first dose of study drug. In this case, set the
 date to the date of first dose.
- If the AE start date month is missing (year is provided) then set the month and day to January 1, unless the year is the same as the year of the first dose. In this case, set the date to the date of first dose.
- If the AE end date day is missing (month and year provided) then set the date to the last day of the month.
- If the AE end date month is missing (year is provided) then set the date to December 31.

• If the year of the AE start date or AE end date are missing, then a query to the site must be made to gather additional information. If the end date and start date are both missing, then no imputation will be done. If the stat date remains missing but the end date is before first dose date, then the AE will be considered before treatment. If the end date is after the first dose, then the AE will be considered to have been treatment emergent.

Imputation rules for missing or partial medication start/stop dates

Start Date:

- If only day is missing, use the first day of the month.
- If day and month are missing, use the first day of the year.
- If day, month, and year are missing use the first day of the year with the same year as the first dose.

End Date:

- If only day is missing, use the last day of the month.
- If day and month are missing, use the last day of the year.
- If day, month, and year are missing assign 'continuing' status to the stop date.

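### SAP 8.4.4 sorts medications by start date alone, so a drug taken throughout the study is tabulated only as prior and some finished courses fit no time-based display

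*SAP*

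**What the plan says.** SAP Section 8.4.4 gives two complementary definitions. For prior medications: "Prior medications are defined as those medications with a start date 28 days prior to the initial screening". For concomitant medications: "Concomitant medications are defined as those medications with a start state later than 28 days prior to the initial screening" (the printed word *state* is read here as *date*). Neither mentions when the drug was stopped or when the study product was given.

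The medications are then tabulated by ATC class and preferred name, per treatment group, in four displays. Three are based on time: "Medications prior to 28 days before the initial screening", "Concomitant medications continued after initial screening" and "Concomitant medications started at or after the initial screening". The fourth collects restricted medications named in the exclusion criteria and covers both classes. On coding, the section states: "Medications used in this study will be coded by using MedDRA version 23.0".

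For incomplete medication start dates, SAP Section 6.0 says: "If day, month, and year are missing use the first day of the year with the same year as the first dose". The same rules give a fully missing stop date a continuing status, so stop dates are part of the data.

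The protocol collects by use. Section 8.1 asks the site to "Review concomitant medication history, including all medications taken within the last 28 days". Section 6.8 then has new drugs and changes to existing ones recorded at every later visit. Footnote 2 of the Schedule of Events, in both documents, lists birth control among concomitant medications.

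**The concern.** A reader goes to a concomitant-medication table to see what subjects were taking when the study product was given and afterwards. In a trial whose primary objective is safety, with 8 active and 2 placebo subjects per cohort, that table helps in judging whether the arms were alike and in reading the adverse events.

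The stated rule answers a different question, namely whether the drug was started before or after a line drawn 28 days before screening. Drugs in use at dosing can be left out of the concomitant displays. Drugs finished before screening can carry the concomitant label without belonging to any time-based display. A drug with an unknown start date is classed by the calendar. The ATC table has no stated coding source.

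**Working it through.** The plan gives no figure to reproduce here. The check applies the SAP's definitions to example histories, which are illustrations and not trial data.

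**1. Where the line falls.** Screening runs from Day -14 to Day -2 (Protocol 8.1). The SAP's study-day formula has no Day 0, so screening is 14 to 2 days before dosing. The cut-off is 28 days before screening:
- screening on Day -14: 28 + 14 = 42 days before dosing
- screening on Day -2: 28 + 2 = 30 days before dosing

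**2. Applying the rule.** A drug is concomitant if its start is later than the cut-off, and prior otherwise. The results are the same at both ends of the screening window.

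| History | SAP class | Time-based display | Taken on or after dosing? |
|---|---|---|---|
| Started 1,000 days before dosing, still taken at study end | prior | first only | yes |
| Started 1,000 days before dosing, stopped 1 day before screening | prior | first only | no |
| 5-day course started 27 days before screening | concomitant | none | no |
| Started 10 days before screening, stopped 1 day before screening | concomitant | none | no |
| Started 10 days before screening, ongoing | concomitant | second | yes |
| Started 10 days after dosing | concomitant | third | yes |

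The first two rows share a class and a display, although only one of the drugs was in use during the study. The 5-day course ends 27 - 4 = 23 days before screening, which is 23 + 14 = 37 or 23 + 2 = 25 days before dosing. It is not prior, did not continue after screening and did not start at or after screening. Unless it is a restricted drug, no planned table has a place for it.

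**3. Unknown start date.** The date is set to 1 January of the dosing year. The drug is concomitant only if 1 January is later than screening minus 28 days, that is, if screening is before 1 January + 28 days = 29 January. Screening up to 28 January gives concomitant, and screening from 29 January gives prior. If screening is in late December and dosing in January, the imputed date falls after screening. A drug already reported at screening then appears in the third display as newly started.

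**4. Contraception as a concrete case.** Inclusion criterion 7 requires contraception for the duration of the study and accepts progestin implants. Footnote 2 of the Schedule of Events counts birth control as concomitant. Under 8.4.4, an implant placed more than 28 days before screening is prior only. The SAP repeats that footnote, so it disagrees with itself.

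**5. Coding.** SAP 8.4.3 and 8.7.1 use MedDRA through its system organ classes and preferred terms. ATC class is not a MedDRA level, and the SAP names no other dictionary for medications.

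**6. Scale of one misplaced subject.** If the table is split by cohort and arm, one subject is 1/8 = 12.5 percentage points in the active arm and 1/2 = 50 points in the placebo arm. If placebo is pooled over five cohorts (5 × 2 = 10), it is 1/10 = 10 points. The documents do not show how many drugs would be affected.

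**The case against.** **Restricted drugs.** A reader might infer that the rule hides H1 antihistamines, beta-blockers, immunosuppressives or oral corticosteroids, which could explain or mask adverse events. The documents do not support this. Exclusion criteria 19 and 20 name all four, and the fourth display tabulates exclusion-listed drugs across both classes, so the position of the dividing line does not matter for them. They are also largely barred at entry and discouraged on study, apart from exemptions.

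**The label on a finished course.** Protocol 6.8 and 8.1 themselves use the word concomitant for drugs taken in the 28 days before screening. Calling such a course concomitant therefore follows the protocol, and an anchor at dosing is a convention that neither document states. This stands. What remains is that the course has no time-based display.

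**Undeclared departure.** A reader might also infer that the SAP departs from a planned analysis without declaring it. Protocol Section 11 contains no medication analysis, so there is nothing to depart from.

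**Kinder readings.** The wording of the prior definition could mean exactly 28 days or within 28 days. The first leaves earlier starts unclassified and the second makes the two classes overlap. The first display supports the reading used here, at or before the cut-off. The second display may have been meant to catch long-standing drugs, but its wording limits it to drugs already classed as concomitant. If it was so meant, the definition contradicts it.

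**Consequence.** The tables are descriptive, SAP Section 7.0 lists all subject data, and a long-standing drug still appears in the first display. A start date with even the year missing should be uncommon. All of this stands and limits the severity.

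**Conclusion.** The definitions in SAP 8.4.4 do not work as written. They place drugs taken throughout the study outside both concomitant displays, leave short non-restricted courses that ended before screening without a time-based display, and let the calendar decide the class when the start date is unknown. MedDRA coding cannot supply the planned ATC table.

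Severity is minor. Only descriptive medication tables are affected, no primary or secondary endpoint depends on them, and nothing is lost from the listings. Contraception is the realistic long-term example in these healthy adults, and the number of drugs affected cannot be estimated from the documents. The conclusion rests on reading the prior definition as a start at or before the 28-day line. The other literal readings leave gaps or overlaps, so they do not rescue the text.

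**What to change.** Rewrite the definitions in SAP 8.4.4 from start and stop dates relative to the date of dosing:

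- **Prior:** stopped before the date of dosing.
- **Concomitant:** taken on or after the date of dosing (stop date on or after it, or ongoing), whatever the start date. Split this into ongoing at dosing and started after dosing, and state which row takes a drug that starts on the dosing date.
- **Unknown start date:** if no stop date falls before dosing, count the drug as ongoing at dosing. Do not let the imputed 1 January decide the class.
- **Displays:** replace the three time-based displays with rows that match these classes, so that every recorded drug has a place. Keep the restricted-medication table as it is.
- **Coding:** replace MedDRA for medications with a drug dictionary that carries ATC classes.

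Use dates and not clock times, because the documents describe only medication dates. The cost is SAP wording, table shells, programming and recoding of the medication terms. No new data are needed from the sites.

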8.6.1 Analysis methods

Refer to section 8.6.5 for analysis methods for secondary endpoints regarding immunogenicity.

8.6.2 Multiplicity

Each immunogenicity endpoint will be analyzed separately, and no multiplicity will be corrected.

8.6.3 Treatment by center interaction analysis (multi-center study)

Five study centers will be involved in the study; however, all subjects will be pooled for secondary efficacy analysis and no treatment by center interaction will be examined.

8.6.4 Analysis of primary efficacy endpoint(s)

Not applicable.

8.6.5 Analysis of secondary efficacy endpoint(s)

Secondary efficacy analysis will be based on microneutralization assay and immunogenicity/ADA assay using blood samples drawn at various predetermined visit days using per-protocol population.

Pharmacokinetic (PK) and Log-Transformed Pharmacokinetic (PK) Parameters will be summarized descriptively by treatment group.

Microneutralization titers will be summarized descriptively by treatment group and compared among treatment groups using Kruskal-Wallis test on log scale. GMT of ADA and GMFR over the initial GMT at baseline will be summarized descriptively by treatment group and compared using Kruskal-Wallis test among cohorts at each study visits. Exploratory pairwise comparisons will also be conducted using Wilcoxon rank sum test; however, resulting p-values will not be corrected for multiplicity. Microneutralization titers on log scale and GMTs for ADA will be plotted by treatment group over study days.

Incidence of the first case of SARS-CoV-2 RT-PCR positive symptomatic illness occurring after dosing through Day 365 will be summarized descriptively by treatment group. Incidence of SARS-CoV-2 RT-PCR

positive severe or critical symptomatic illness occurring after dosing through Day 365 will be summarized descriptively by treatment group.

Incidence of COVID-19 related Emergency Department visits occurring after dosing through Day 365 will be summarized descriptively by treatment group.

Due to the small number of subjects in this study, negative hypothesis tests should be interpreted carefully as the study has not been powered to detect differences between groups.

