- 18. Active drug or alcohol use disorder or dependence that, in the opinion of the investigator, would interfere with adherence to study requirements
- 19. Use of H1 antihistamines or beta-blockers within 5 days of dosing
- 20. Use of any prohibited medication within 28 days prior to screening or planned use during the study period
 - Note: Prohibited medications include immunosuppressives (except Nonsteroidal Anti-Inflammatory Drugs [NSAIDS]); immune modulators; oral corticosteroids (topical/intranasal steroids are acceptable); anti-neoplastic agents
- 21. Any specific condition that in the judgment of the investigator precludes participation because it could affect subject safety
- 22. Plans to enroll or is already enrolled in another clinical trial* that could interfere with safety assessment of the investigational product at any time during the study period
 - Note: Includes trials that have a study intervention such as a drug, biologic, or device
- 23. Is a study site employee or staff
 - Note: Site employees or staff include the Pis and sub-investigators or staff who are supervised by the PI or Sub-Investigators
- 24. Received an approved COVID-19 vaccine (subjects can receive an approved COVID-19 vaccine after completing their Day 90 visit. For Cohort 5, subjects who received a COVID-19 vaccine within 14 days prior to enrollment are excluded.

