5.0 Analysis Populations

Full Analysis Set (FAS)/Intention-To-Treat population (ITT)

An intent-to-treat population will consist of all subjects randomized and will be analyzed as randomized.

Safety population (Safety)

All subjects who received study product will be included in the safety population and analyzed as treated.

Per-Protocol population (PP)

The Per-protocol population will consist of all subjects in the ITT population who were free from major protocol violations. Patients will be included in the analysis according to the treatment group they are randomized to.

Pharmacokinetics (PK) population

The PK population will consist of all subjects who complete ADM03820 injection and have sufficient evaluable PK samples for the estimation of PK parameters. Subjects in the PK population will be analyzed in the dose cohort and treatment group corresponding to the study drug that they have received.

Protocol deviations

Protocol deviation data will be captured in the clinical trial management system. Extracts of all protocol deviations will be reviewed periodically and prior to any interim or final analyses. All protocol deviations and the exclusion of participants from analysis sets will be identified prior to unblinding through clinical review and input provided by the sponsor using supportive participant listings provided by the ICON GPHS statistician based upon data recorded in the clinical trial management system.

Further, deviations from the protocol will be classified as major or minor. Classification of major and minor protocol deviations is determined prior to participant enrollment and is outlined in detail in the protocol deviation criteria documentation managed by the clinical trial management team.

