7.0 Statistical Methods

General statistical conventions

All statistical procedures will be completed using SAS version 9.4 (or higher), R version 4.0.0 (or higher), or Phoenix WinNonLin 8.3.1 (or higher).

Unless otherwise stated, all statistical testing will be two-sided and will be performed using a significance (alpha) of 0.05. Two-sided 95% confidence intervals (CI) will be provided when relevant.

Continuous variables will be summarized using descriptive statistics, including number of subjects (n), mean, median, standard deviation (SD), interquartile ranges (IQR), minimum, and maximum.

For categorical variables, summaries will include counts of subjects and percentages. Percentages will be rounded to one decimal place.

For summary purposes, baseline will be defined as the last available pre-dose value. All summaries will be presented by treatment group, unless otherwise specified.

All subject data, including those derived, will be presented in individual subject data listings. Unless otherwise stated, unscheduled visit results will be included in date/time chronological order, within patient listings only. All listings will be sorted by subject ID, date/time and visit. The treatment group will be stated on each listing. Unless otherwise stated, data listings will be based on FAS.

Unscheduled data points will not be used in any summary tables separated by visit but will be presented in each listing as appropriate.

Subject disposition

Subject disposition information will be summarized by dosing cohort, treatment group and overall. The number and percentage of subjects who are enrolled, who complete the study, and who withdraw early from the study will be presented.

The primary reasons for early withdrawal will also be tabulated, including withdrawal by subject, physician decision, lost to follow-up, major protocol deviation or other.

The number of subjects enrolled will be used as the denominator for the percentage calculation. Subject disposition will be listed.

The number and percent of subjects in each analysis set will also be tabulated. A listing of each subject excluded from an analysis population will be listed as well as the reason why they were excluded from the population.

Treatment Misallocations: if a subject is

- Randomized but withdrawn prior to dosing, then they will be replaced and will not be included in any analysis.
- Randomized but receive incorrect treatment, they will be reported under the treatment they actually

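### SAP 8.6.5 compares neutralising titres without using the pre-dose value or any vaccination or infection rule, so 600 mg contrasts with other active cohorts are confounded and Day 120 to 180 titres can be vaccine antibody

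*SAP*

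**What the plan says.** SAP 8.6.5, in the per-protocol population: "Microneutralization titers will be summarized descriptively by treatment group and compared among treatment groups using Kruskal-Wallis test on log scale". A baseline-relative measure appears only in the ADA sentence: "GMT of ADA and GMFR over the initial GMT at baseline will be summarized descriptively by treatment group". It is followed by: "Exploratory pairwise comparisons will also be conducted using Wilcoxon rank sum test", with no multiplicity correction and no statement whether these tests cover MN. The general conventions define baseline ("For summary purposes, baseline will be defined as the last available pre-dose value") but attach no change score or covariate to MN.

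On who may enter, Protocol 5.2 waives exclusion 15 (positive SARS-CoV-2 serology) for Cohort 5. Exclusion 24 bars vaccinated subjects in Cohorts 1-4, but then adds: "For Cohort 5, subjects who received a COVID-19 vaccine within 14 days prior to enrollment are excluded". Cohort 5 is the only 600 mg group (Protocol Table 1). Appendix A footnote 18 says its serology is not tested, so pre-dose MN is the only planned measure of its prior immunity. Protocol 7.5.1.1 still requires a negative antibody test with no Cohort 5 exception, and Protocol 5 allows exemptions from eligibility criteria.

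On follow-up, exclusion 24 and Protocol 8.3 permit COVID-19 vaccination after the Day 90 visit. MN is sampled pre-dose and on Days 2, 15, 30, 60, 90, 120, 150 and 180. The analysis set is defined thus: "The Per-protocol population will consist of all subjects in the ITT population who were free from major protocol violations".

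**The concern.** A Kruskal-Wallis test depends only on ranks, which the log scale does not change, so the planned test is of the unadjusted titre. Two things other than the drug can move that titre.

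(a) Entry immunity. It is permitted in one dose group and excluded in the others. Any MN contrast of Cohort 5 with other active cohorts, by cohort or by dose level, carries both dose and pre-existing antibody. Own antibody can exaggerate or imitate a dose response at 600 mg.

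(b) Vaccination or infection on study. Vaccine antibody lifts late titres in active and placebo alike. This hides residual drug activity and flattens the durability plot. If uptake differs between cohorts, it also biases cohort contrasts. The per-protocol set is unlikely to remove permitted vaccination, although the deviation criteria are in a separate document.

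**Working it through.** **Step 1. The plan's own figures.** The only design numbers (Protocol 11.1; SAP Sample Size and Power) concern safety events in 8 active subjects. All three reproduce: 1 − 0.85^8 = 0.728; 1 − 0.5^8 = 0.996; 1 − 0.025^(1/8) = 0.369. None concerns MN. The documents give no MN titre, SD, immune share or vaccine uptake, so every size below rests on assumptions.

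**Step 2. Exposure, from the documents.** Allocation is 8:2 in each of five cohorts. Cohort 5 supplies 8/40 = 20% of actives and 2/10 = 20% of placebos, so entry immunity is balanced in a pooled active-versus-placebo comparison. It supplies all of the 600 mg group and none of the 150 or 300 mg groups. Visits after Day 90: 3 of 8 post-dose MN visits.

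**Step 3. Entry immunity, equal drug titre in all cohorts.** Assumed: titre = drug + own antibody, floor 10; log2 SD 1 (drug) and 1.5 (own); 8 actives per cohort; two-sided 0.05; 6,000 simulated trials.

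| Share immune in Cohort 5 | Own GMT | Drug GMT | Kruskal-Wallis, 5 active cohorts | Wilcoxon, Cohort 5 v pooled 300 mg (8 v 24) | Apparent GMT ratio |
|---|---|---|---|---|---|
| 75% | 320 | 3200 | 5% | 6% | 1.1 |
| 75% | 320 | 1280 | 8% | 13% | 1.3 |
| 50% | 160 | 320 | 8% | 15% | 1.3 |
| 75% | 320 | 320 | 31% | 53% | 1.9 |
| 100% | 640 | 320 | 90% | 98% | 3.5 |

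- A different model, in which immunity shifts log10 titre by 0.3 to 1.0, gives Kruskal-Wallis false rejection of 6-34% with half of Cohort 5 immune and 13-100% with all immune.
- Restricted to Cohorts 1-4, the test rejects in 4-5%.
- With pooled placebo as a further group, the overall test rejects in 99.6-100% whatever the immunity. The harm then lies in the GMTs, plots and any pairwise tests.
- If drug titre is proportional to dose (true 600/300 ratio 2.0), the raw ratio in the last four scenarios is 2.3-4.8. Active-only rejection rises from 81% with nobody immune to 91-100%. Cohorts 1-4 alone have about 40% power.

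**Step 4. Vaccination after Day 90, Cohorts 1-4, equal uptake.** Assumed: residual drug GMT 80, placebo at 10, vaccine GMT 320 (log2 SD 1.5). Values kept = 32 × (1 − uptake).

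| Uptake | Active GMT | Placebo GMT | Ratio | Power, 150 v 300 mg (40 v 80), raw | Same, after exclusion | Active values kept |
|---|---|---|---|---|---|---|
| 0% | 80 | 10 | 8.0 | 40% | 39% | 32 |
| 20% | 113 | 20 | 5.6 | 19% | 31% | 26 |
| 50% | 190 | 56 | 3.4 | 8% | 14% | 16 |
| 80% | 319 | 162 | 2.0 | 6% | 3% | 6 |

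With equal uptake the active-only type I error stays at about 4%. With uneven uptake in Cohorts 1/2/3/4, false rejection is 8% (60/60/40/40), 25% (70/70/30/30) or 59% (80/80/20/20). Excluding post-vaccination values returns these to about 3%.

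**Step 5. Would baseline adjustment repair (a)?** Not reliably.

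- Log fold rise holds 4-6% if immunity multiplies the titre, but under the Step 3 additive model Kruskal-Wallis on log fold rise falsely rejects in 32-100%.
- Linear change holds 4-5% under noise-free additive titres with stable own antibody. With assay SD 0.5 log2, its dose-proportional power falls to 67% and about 48-50% in the last two Step 3 scenarios, and null pairwise rejection in the last is about 10-11%.
- If own antibody halves, linear change falsely rejects in 16% and 55% of trials in those two scenarios (Kruskal-Wallis). At least one Cohort 5 change is zero or negative in 87% and nearly 100%, which a log-scale summary cannot take.

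**The case against.** The strongest reply is that part (a) depends on an undefined term. The SAP separates the two words elsewhere ("Subject disposition information will be summarized by dosing cohort, treatment group and overall"), and 8.6.5 uses cohorts for ADA but treatment groups for MN. If treatment group means pooled active versus placebo, part (a) disappears from that test. This stands, and the verdict is conditional on it. A reader might infer that active versus placebo is also confounded by entry immunity; the 8:2 allocation in every cohort rules that out.

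Second, much is already visible. All subject data are listed, MN is plotted over study days with a pre-dose point, RT-PCR positives are listed, and the pairwise tests are labelled exploratory. That helps a careful reader, but leaves the handling to be chosen after the data are seen. The SAP's own caution ("negative hypothesis tests should be interpreted carefully as the study has not been powered to detect differences between groups") covers negative tests only, whereas entry immunity can produce positive ones.

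Third, exclusion costs data. At 80% uptake its power is 3% against 6% raw, and only 69% of simulated trials are testable. This stands. The gain is a titre that reflects the drug and a controlled error rate, not much power.

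A reader might also infer that a fold rise from baseline, as for ADA, would cure the problem. Step 5 shows that this depends on how drug and own antibody combine, which the documents do not say.

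**Conclusion.** The concern holds as a gap in SAP 8.6.5. The MN comparison ignores the pre-dose value and has no rule for values after vaccination or infection. Contrasts of Cohort 5 with other active cohorts are confounded with entry immunity if the test is by cohort or dose level, and titres at Days 120, 150 and 180 can be vaccine antibody.

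Confidence is high for the missing rules and low for the size. Under the assumed inputs, false rejection in the active-only test runs from about 5% (drug titre far above own titre) to 90% (all immune at twice the drug titre). Equal uptake of 20/50/80% cuts a ratio of 8 to about 5.6/3.4/2.0, and uneven uptake gives false rejection of about 8-60%.

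A reader might infer that any 600 mg signal would be spurious. The documents do not support that: if drug titre dominates, the bias is negligible, and if titre follows dose, the effect is mainly exaggeration. Nor do they show that uptake was uneven. MN is a secondary, unpowered endpoint, and the primary safety objective is unaffected. The change should be made, but the trial does not depend on it.

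**What to change.** In SAP 8.6.5:

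1. Exclude MN values after the first post-dose COVID-19 vaccination from the main MN summaries, plots and tests, with an all-values sensitivity analysis. Query partial vaccination dates instead of relying on the SAP's medication-date imputation.
2. Show MN results with and without values after RT-PCR-positive infection. Do not exclude these outright, because infection is a post-dose outcome that the product may affect.
3. State which groups enter the MN test and whether the pairwise tests cover MN. Make the between-cohort test on Cohorts 1-4 the comparison free of this confounding. Show Cohort 5 separately with its pre-dose MN distribution, and state that 600 mg MN contrasts are confounded by entry immunity.
4. Treat any baseline-adjusted Cohort 5 result (linear change or log fold rise) as a sensitivity analysis only, with its assumption stated.

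Separately, Protocol 7.5.1.1 must be reconciled with exclusion 15 and Appendix A footnote 18.

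Cost: SAP wording plus one protocol reconciliation, and no new data. Vaccination dates should already be recorded under Protocol 6.8 and 8.3; confirm this. The price is fewer late values (about 6 of 32 actives in Cohorts 1-4 at 80% uptake) and low power there. The Cohorts 1-4 test has about 40% power under dose-proportionality, against about 81% with Cohort 5 included and nobody immune. Asymptomatic infection will still be missed, because on-study RT-PCR is triggered by symptoms.
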